9.7.3.2. SCRI Design

SCRI design with post-vaccination control interval will compare the incidence of prespecified outcomes occurring in the risk interval following ABRYSVO vaccination with the incidence of prespecified AESIs occurring during the post-vaccination control interval.

In order to account for the self-matched design, a conditional Poisson regression model will be used to estimate relative incidence and 95% CIs. The dependent variable will be the

number of events occurring during the risk or control window. The independent variables in all the models will be the type of window (risk or control), and the person-time in each considered window, which will be handled as an offset term. The SCRI inherently adjusts for both measured and unmeasured time constant factors such as sex and chronic health conditions with onset before the start of follow-up. Time-varying confounders may be included as covariates in regression models. Outcomes for which the SCRI design will be a complementary design, and corresponding risk windows for such outcomes are described in Table 1.

As noted in Section 9.2.1, individuals in the SCRI design will be required to have full accrual of data to define the outcome in the risk and control intervals combined. If an outcome of interest (e.g., cardiac outcome) substantially increases the mortality risk, death may prevent individuals from accruing the full follow-up period, leading to their exclusion from the SCRI study. To evaluate this possibility, the 30-day CFR will be calculated for each outcome. Outcomes with a high 30-day CFR (e.g., >20%) will be considered for further adjustment in the SCRI design. Approaches may include using the Farrington adjustment as the primary analysis or extending follow-up periods to include individuals who die following an outcome of interest in the SCRI analyses. The final 30-day CFR threshold, and details of the adjustment method, will be specified in the SAP.

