9.1.2. Self-controlled Risk Interval (SCRI) Design

[figure not shown]
A SCRI design will be used for a subset of study outcomes that meet the necessary study design assumptions, as a complementary analytic approach. The assumptions for a SCRI design include that the outcome must have acute onset and short latency, as well as a relatively well-defined risk interval. The assumptions underpinning the SCRI also require that occurrence of the outcome does not affect the probability of exposure. Table 1 in Section 9.3 indicates outcomes for which a SCRI analysis is deemed a valid approach.

The SCRI design uses information from cases (i.e, vaccinated individuals who experience an outcome) to compare the incidence of an outcome in the risk interval following vaccination to the incidence in a post-vaccination control interval within the same individual.^{22, 23}

Unlike the comparative cohort design, which may suffer from potential vaccine exposure under-ascertainment and misclassification as well as potential residual confounding, the SCRI design is a within person analysis that implicitly controls for time invariant confounders. Time varying confounders still need to be controlled for but with short, defined risk windows, the risk of time varying confounding is limited.

Risk intervals will be applied starting on the day after vaccination (Day 1), for a duration of time specific to each outcome; Table 1 in Section 9.3 defines the risk interval proposed for each outcome. A prespecified post-vaccination control interval will be used for each outcome of interest. The post-vaccination control interval will occur after the risk interval associated with ABRYSVO administration to avoid potential differential reporting of outcome in the pre- and post-vaccination periods. The risk and control intervals are based on a review of the published literature and precedence from previous studies of vaccine safety (see Table 1). As an example, the SCRI design with 42-day risk interval and 42-day post-vaccination control interval for Guillain-Barré syndrome (GBS) is presented in Figure 3 below.

Figure 3 Self-controlled Risk Interval Design

PFIZER CONFIDENTIAL CT24-WI-GL02-RF02 5.0 Non-Interventional Study Protocol Template For Secondary Data Collection Study 01-Aug-2023 Page 23 of 72

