9.2.1. Inclusion Criteria

Patients meeting the following criteria will be included in the study:

- Vaccinated Cohort: Vaccination with ABRYSVO
- *Unvaccinated Cohort:* No vaccination with ABRYSVO or other vaccines on the index date
- *Unvaccinated Cohort:* No vaccination with any RSV vaccine in the 12-months prior to index
- Each population of immunocompromised or renally impaired or hepatically impaired individuals must meet the population-specific inclusion criteria in Section 9.2.1.1, Section 9.2.1.2, and Section 9.2.1.3, respectively
- Age 60 years and older at index date
- A minimum of 12 months of administrative enrollment history prior to index in one of the selected data sources to ensure adequate characterisation of medical history
- A minimum of one day of follow up post-index
- For analyses of outcomes assessed with the SCRI design, the following additional criteria must be met. Note that the study population for each outcome-specific analysis will thus be different
 - a. Have received ABRYSVO
 - b. Have experienced an event of interest during the risk or control interval
 - c. Have full accrual of data used to define the event in the risk and control intervals combined, after accounting for any data lag and timing of data extraction

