9.7.4. Sensitivity Analyses

As feasible, sensitivity analyses, as well as analyses to evaluate potential bias, may include, but are not necessarily limited to:

- Comparative cohort design with extended risk windows for the acute outcomes to assess potential outcome under-reporting and misclassification
 - The exception will be atrial fibrillation and supraventricular arrhythmias where shorter risk windows of 0-3 days (as well as 0-1 days and 0-30 days) will be considered to allow for greater consistency with the ongoing ABRYSVO safety study in the Veterans Affairs population (C3671037). Further details on alternative risk intervals will be provided in the SAP.
- SCRI with alternative risk and control intervals to assess potential exposure misclassification. In addition, to allow for greater consistency across ongoing ABRYSVO vaccine safety studies, specifically C3671031 and C3671037, the following risk intervals will be applied as sensitivity analyses for the following AESIs:
 - GBS: risk interval 1-21 days⁵⁹
 - Acute disseminated encephalomyelitis: risk interval 5-28 days ⁶⁰
 - Transverse myelitis: risk interval 1-21 days ^{59, 61}

PFIZER CONFIDENTIAL

CT24-WI-GL02-RF02 5.0 Non-Interventional Study Protocol Template For Secondary Data Collection Study 01-Aug-2023 Page 48 of 72

- A SCRI analysis may also be considered for atrial fibrillation and supraventricular arrhythmias with risk intervals of 0-3 days, 0-1 days and 0-30 days to align with the planned SCRI analysis from study C3671037. Further details on alternative risk and control intervals will be provided in the SAP.
- SCRI with pre-vaccination control interval. If vaccination is deferred while unwell with symptoms related to outcomes, this may violate the assumption of the SCRI design that an outcome event should not alter the probability of subsequent exposure to vaccination. Defining a separate pre-vaccination window can assess these design assumptions and ensure that they are not violated.
- SCRI with a washout period between risk and control intervals, within the subset of outcomes for which an increased risk is detected
- For outcomes with CFR >20%, SCRI analysis incorporating Farrington adjustment or extending follow-up after death for full length of risk and control window
- Use of narrow and broader definition algorithms for outcomes to assess outcome misclassification (comparative cohort and SCRI)

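### The SCRI analysis excludes cases who die before the control interval ends, which biases its IRR downward, and the 30-day fatality check is too short for the longer windows

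*Protocol*

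**What the plan says.** Section 9.2.1, criterion (c), requires SCRI cases to "Have full accrual of data used to define the event in the risk and control intervals combined", after allowing for data lag and extraction timing. Section 9.7.3.2 repeats the requirement and names its consequence: "death may prevent individuals from accruing the full follow-up period, leading to their exclusion from the SCRI study".

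The safeguard in 9.7.3.2 is a screen on 30-day case fatality: "To evaluate this possibility, the 30-day CFR will be calculated for each outcome". Then: "Outcomes with a high 30-day CFR (e.g., >20%) will be considered for further adjustment in the SCRI design". The adjustments named are the Farrington method, possibly as the primary analysis, or follow-up extended to include people who die. What remains open is stated: "The final 30-day CFR threshold, and details of the adjustment method, will be specified in the SAP". The 30-day horizon is not among the open items.

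Section 9.7.4 lists a matching sensitivity analysis: "For outcomes with CFR >20%, SCRI analysis incorporating Farrington adjustment or extending follow-up after death for full length of risk and control window".

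Section 9.1.2 places the control interval after the risk interval and gives one worked example, Guillain-Barré syndrome, with 42 days of each. Table 1 lists risk windows for the other SCRI outcomes but no control lengths.

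**The concern.** The survival requirement does not fall equally on the two intervals. An event soon after vaccination must be followed by a long survival before it counts; an event late in the control interval needs almost none. Fatal cases are lost mainly from the risk interval, so the SCRI incidence rate ratio moves downward, which in a safety study is the direction that hides harm.

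The protocol recognises that deaths cause exclusion, but the screen it relies on has two weaknesses. It counts deaths to 30 days after the event, while for the longer windows exclusion continues well past 30 days. It also leads only to adjustment being considered, and nothing is planned for an outcome below the threshold.

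The SCRI estimates are meant to offset exposure misclassification and residual confounding in the cohort design (section 9.9), and they are pooled across data sources (section 9.7.3.3). A bias with the same sign in every source does not average out on pooling.

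**Working it through.** The plan states no figure for this bias, so there is none to reproduce.

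**Inputs from the protocol.** Risk interval days 1 to 42 and control interval days 43 to 84 (9.1.2 example); control after risk (9.1.2); survival to the end of both intervals needed for inclusion (9.2.1 criterion (c), 9.7.3.2); screen at 30 days, example threshold 20% (9.7.3.2).

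**Assumptions.** 30-day CFR of 5% to 20%; five patterns of death timing; one event per person, spread evenly within each interval; control length equal to risk length wherever the protocol gives none.

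**Step 1: survival needed.** A case on day t is kept only if alive on day 84, that is 84 − t days later.
- Risk interval: t = 1 gives 83 days, t = 42 gives 42 days.
- Control interval: t = 43 gives 41 days, t = 84 gives 0 days.

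**Step 2: bias factor.** With S(u) the probability of surviving u days after the event,

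B = [mean of S(84 − t) over t = 1..42] / [mean of S(84 − t) over t = 43..84].

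The expected IRR is B times the true IRR. S cannot rise with u, so B is at most 1. It equals 1 when all deaths fall on the event day.

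**Step 3: one case in full.** Constant hazard, 30-day CFR 20%: S(u) = 0.8^(u/30). The mean over u = 42..83 is 0.631 and over u = 0..41 is 0.862, so B = 0.631/0.862 = 0.732.

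**Step 4: B for 42+42 days.**

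| Death timing (assumed) | CFR 5% | 10% | 15% | 20% |
|---|---|---|---|---|
| Constant hazard | 0.931 | 0.863 | 0.797 | 0.732 |
| Weibull, shape 0.5 | 0.967 | 0.932 | 0.897 | 0.861 |
| Uniform over 30 days | 0.981 | 0.961 | 0.939 | 0.916 |
| Uniform over 7 days | 0.995 | 0.990 | 0.983 | 0.977 |
| All on event day | 1.000 | 1.000 | 1.000 | 1.000 |

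A simulation of 2,000,000 cases under constant hazard agrees. For true IRRs of 1, 1.5, 2 and 3, the exclusion rule returns 0.86, 1.29, 1.73 and 2.59 at CFR 10%, and 0.73, 1.10, 1.47 and 2.20 at CFR 20%. Keeping the fatal cases with planned windows (CFR 20% runs) returns 1.00, 1.50, 2.00 and 3.01.

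**Step 5: what a 30-day horizon misses.** Under constant hazard, a 30-day CFR of 10% means 1 − 0.9^(83/30) = 25% dead by day 83 after the event, and a CFR of 20% means 46%. Under the Weibull pattern the figures are 16% and 31%.

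**Step 6: other windows (Table 1, equal control length assumed).**

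| SCRI outcomes | Risk + control | Longest survival needed | B at CFR 20%, constant hazard |
|---|---|---|---|
| 42-day outcomes | 84 days | 83 days | 0.732 |
| Coagulation disorders, cutaneous vasculitis | 56 days | 55 days | 0.812 |
| Myocarditis | 42 days | 41 days | 0.855 |
| 15-day outcomes | 30 days | 29 days | 0.894 |
| Pericarditis | 28 days | 27 days | 0.901 |

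Generalised convulsion starts on day 0, so its span is slightly longer than 84 days. The 30-day horizon is too short for the first three rows. It is adequate for the last two and for shorter windows, but B is still below 1 there.

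**Step 7: error of the remedy.** Planned windows count control time after deaths from unrelated causes. With background hazard h, the IRR is multiplied by [mean of exp(−ht) over t = 1..42] / [mean over t = 43..84]. Assumed annual mortality of 5%, 10% and 20% gives 1.006, 1.012 and 1.026. Mortality of 10% over 84 days (about 35% per year) gives about 1.05.

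**The case against.** The strongest reply is that the protocol already sees the problem. It calculates a CFR for every outcome, names two remedies, marks 20% as an example, and leaves the threshold and method to the SAP. All of that is true, and a low SAP threshold would catch many outcomes. It would not change the 30-day horizon or the survival-based inclusion rule, both of which the protocol fixes.

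Four stronger readings are tempting, and the documents do not support them.

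- A reader might infer that every SCRI case faces an 84-day survival requirement. Only the 42-day outcomes do, and a control length is stated only for Guillain-Barré syndrome. Stroke, myocardial infarction and pulmonary embolism fall under a 28-day window, and myocarditis under 21 days.
- A reader might infer that outcomes just under 20% are certain to go unadjusted. Section 9.7.4 does state 20% without qualification, but in a permissive list, and 9.7.3.2 leaves the final value open.
- A reader might infer a known, large bias for named outcomes. No CFR or death timing is given for any outcome, so the size is entirely assumed.
- A reader might infer that the study loses fatal early events. It does not: the primary cohort design follows each person to the outcome and so counts fatal cases, and all-cause death is itself a cohort outcome.

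The difference between 9.7.3.2 (Farrington possibly primary) and 9.7.4 (sensitivity) is an ambiguity rather than a contradiction, because both passages are permissive. The remedy also has its own upward error (step 7), which could exceed the bias removed where fatality is very low or deaths are nearly immediate.

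**Conclusion.** The point holds for the complementary SCRI analysis. Excluding cases who die before the combined intervals end biases the IRR downward unless deaths fall on the event day. The direction follows from the order of the intervals and needs no outside data.

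The size does depend on assumed death timing. At 30-day CFR 10% to 20% with 42+42 days, the factor runs from about 1.00 to 0.86 (CFR 10%) or 0.73 (CFR 20%); at CFR 5% it is 0.93 to 1.00.

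The 30-day screen is shorter than the exclusion span for the 42-day outcomes and, if control length equals risk length, for the 28-day and 21-day outcomes. For spans of about 30 days or less the horizon is adequate and only the exclusion itself remains at fault. The primary cohort estimates are not affected.

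**What to change.** 1. In 9.2.1, reword criterion (c) so that full accrual refers only to data lag and extraction date, and state that death after the event is not a reason for exclusion. Align 9.7.3.2.
2. Keep cases who die, with the planned full-length risk and control windows as person-time. Sections 9.7.3.2 and 9.7.4 already allow this. Report the survivors-only version as a sensitivity analysis.
3. If a CFR screen is kept to decide on the Farrington adjustment, calculate it over each outcome's full risk plus control span instead of 30 days.
4. Give the adjustment the same role, primary or sensitivity, in 9.7.3.2 and 9.7.4. Which role it takes is the sponsor's choice; this point does not require demoting it.

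The cost is wording in three sections. No new data are needed, and more of the rare cases are kept. The downside is the over-counted control time in step 7: about 0.6% to 2.6% upward at assumed annual background mortality of 5% to 20%, and about 5% at roughly 35% per year.

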9.7.3.3. Meta-analysis

For both the comparative cohort and SCRI designs, an appropriate random-effects metaanalytic method will be applied to the main estimates from each data source to obtain a combined effect estimate. The heterogeneity across data sources will be checked, and a forest plot will be produced with the data sources and the pooled estimate.

9.7.4. Sensitivity Analyses

As feasible, sensitivity analyses, as well as analyses to evaluate potential bias, may include, but are not necessarily limited to:

- Comparative cohort design with extended risk windows for the acute outcomes to assess potential outcome under-reporting and misclassification
 - The exception will be atrial fibrillation and supraventricular arrhythmias where shorter risk windows of 0-3 days (as well as 0-1 days and 0-30 days) will be considered to allow for greater consistency with the ongoing ABRYSVO safety study in the Veterans Affairs population (C3671037). Further details on alternative risk intervals will be provided in the SAP.
- SCRI with alternative risk and control intervals to assess potential exposure misclassification. In addition, to allow for greater consistency across ongoing ABRYSVO vaccine safety studies, specifically C3671031 and C3671037, the following risk intervals will be applied as sensitivity analyses for the following AESIs:
 - GBS: risk interval 1-21 days⁵⁹
 - Acute disseminated encephalomyelitis: risk interval 5-28 days ⁶⁰
 - Transverse myelitis: risk interval 1-21 days ^{59, 61}

PFIZER CONFIDENTIAL

CT24-WI-GL02-RF02 5.0 Non-Interventional Study Protocol Template For Secondary Data Collection Study 01-Aug-2023 Page 48 of 72

- A SCRI analysis may also be considered for atrial fibrillation and supraventricular arrhythmias with risk intervals of 0-3 days, 0-1 days and 0-30 days to align with the planned SCRI analysis from study C3671037. Further details on alternative risk and control intervals will be provided in the SAP.
- SCRI with pre-vaccination control interval. If vaccination is deferred while unwell with symptoms related to outcomes, this may violate the assumption of the SCRI design that an outcome event should not alter the probability of subsequent exposure to vaccination. Defining a separate pre-vaccination window can assess these design assumptions and ensure that they are not violated.
- SCRI with a washout period between risk and control intervals, within the subset of outcomes for which an increased risk is detected
- For outcomes with CFR >20%, SCRI analysis incorporating Farrington adjustment or extending follow-up after death for full length of risk and control window
- Use of narrow and broader definition algorithms for outcomes to assess outcome misclassification (comparative cohort and SCRI)
- Descriptive analyses will be conducted to assess whether there is differential receipt of other vaccines in the follow up period between the vaccinated and unvaccinated cohort (comparative cohort design) and between the risk and control intervals (SCRI design). Differential receipt of vaccines during follow up may introduce potential time varying confounding. If differential patterns of vaccination during follow up are observed, the following approaches may be considered:
 - Comparative cohort analysis with censoring at receipt of another vaccine during follow-up
 - SCRI with analyses stratified by those who did and did not receive vaccinations during the risk or control interval
 - For individuals with receipt of other vaccines close to index (e.g.,30 or 45 days prior to index), comparative cohort and SCRI analyses will be repeated excluding those individuals
- Quantitative bias analysis to assess potential unmeasured confounding (comparative cohort)
- Negative control outcome analyses will be considered to assess potential unmeasured confounding, selection bias, and misclassification bias (for both comparative cohort and SCRI designs). As different AESIs may be associated with different care and medical encounter patterns reflecting different bias structures, careful consideration should be given to which negative controls are appropriate for which AESI analyses. As such, several negative controls may be considered for inclusion, including, but not limited to, accidental poisoning, appendicitis, cataracts, or non-vertebral fractures. Further details on the choice of negative control outcomes will be described in the SAP.

Further details and any additional sensitivity analyses that may be conducted will be described in the SAP.

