7. RATIONALE AND BACKGROUND

RSV is a major cause of respiratory illness in both infants and older adults.¹ Older adults are at higher risk of RSV illness and have a greater risk of hospitalisation and mortality with RSV compared with younger adults.²⁻¹⁰ Each year in Europe, it is estimated that RSV causes more than 270,000 hospitalisations and about 20,000 deaths in individuals 60 years and older.¹¹

RSV illness commonly occurs in individuals with existing comorbidities, which are exacerbated due to RSV exposure.^{10, 12-14} According to a study across 28 EU countries, RSV infection among older adults, especially those with underlying health conditions, is a significant contributor to acute respiratory infection (ARI) related hospitalisation.¹⁵ Older adults with compromised immune systems, or pre-existing conditions such as kidney disorders, liver disorders, diabetes, heart disease, and lung disease, face the highest risk of contracting severe RSV infection, and therefore, are most likely to benefit from vaccination.^{16, 17} RSV has been recognized as a significant cause of severe illness in immunocompromised populations, including hematopoietic stem cell transplantation recipients, patients undergoing intensive chemotherapy, and lung transplant patients.¹

Immunocompromised individuals, who are susceptible to severe, persistent RSV infections, are known to have the highest morbidity and mortality from RSV.^{12-14, 18} Other older adult patient populations at high risk of both infection and severe RSV illness include those who with renal or hepatic impairment.¹⁹

On 23 August 2023, PF-06928316 (ABRYSVO) was approved by the European Commission for active immunisation of adults 60 years of age and older for the prevention of LRTD

PFIZER CONFIDENTIAL CT24-WI-GL02-RF02 5.0 Non-Interventional Study Protocol Template For Secondary Data Collection Study 01-Aug-2023 Page 18 of 72 caused by RSV. On 31 May 2023, the FDA approved ABRYSVO for active immunization for the prevention of LRTD caused by RSV in adults 60 years of age and older.

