9.2.4. Study Period

The study period will start from 23 August 2022 to allow at least 12 months of administrative enrolment before vaccination with vaccination possible from the date of approval in the EU. Data collection will extend through a minimum of three vaccination seasons (2023, 2024, and 2025). Patient follow-up will last for up to 12 months post-vaccination depending on the outcome; therefore, data collection will extend through the end of 2026, at a minimum. Vaccine uptake will be periodically monitored to inform the overall length of the study period, and additional vaccination seasons (with 12-month post-vaccination follow-up) may be added based on vaccine uptake and exposure accrual. Time lags for data availability will be taken into account for analysis and reporting purposes.

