9.5. Study Size

The study will be conducted in a source population of the participating population-based electronic healthcare data sources from the VAC4EU network.

Table 2 shows the sample size calculations for select outcomes (i.e, anaphylaxis, GBS, and arrhythmia) using the comparative cohort design, assuming a two-sided alpha level of 0.05, an equal number of individuals for the vaccinated and unvaccinated cohorts, and a power of 80% across a range of IRRs. Given a lack of published background incidence rates for outcomes among the specific populations of interest (i.e, adults aged 60 and older who are immunocompromised or renally impaired or hepatically impaired), published incidence rates from general populations aged 60 years and older in VAC4EU databases⁴² were used to estimate rates in the unvaccinated cohort. As an example, to detect an IRR of 2 for arrhythmia with a power of 80% and two-sided alpha level of 0.05, a sample size of 1,178 vaccinated individuals and 1,178 unvaccinated individuals is needed. This assumes a background rate of 2,000 arrythmia events per 100,000 person-years among the unvaccinated individuals.

Outcome	Background rate	Background rate	Incidence rate	Samp	le size
	per 100,000 person-years ^a	per person during risk interval ^b	ratio	Vaccinated cohort	Unvaccinated cohort
Anaphylaxis	10	0.0000005	2	47,093,279	47,093,279
			3	15,697,760	15,697,760
			5	5,886,660	5,886,660
			10	2,131,795	2,131,795
	15	0.0000008	2	29,433,300	29,433,300
			3	9,811,100	9,811,100
			5	3,679,163	3,679,163
			10	1,332,372	1,332,372
Guillain-	6	0.0000069	2	3,412,557	3,412,557
Barré syndrome			3	1,137,519	1,137,519
Synarollic			5	426,570	426,570
			10	154,478	154,478
	10	0.0000115	2	2,047,534	2,047,534
			3	682,512	682,512
			5	255,942	255,942
			10	92,687	92,687
Arrhythmia	2,000	0.0200000	2	1,178	1,178
			3	393	393

Table 2Number of Individuals Needed to Detect Different Rate Ratios for Selected
Outcomes with a Range of Background Rates

PFIZER CONFIDENTIAL CT24-WI-GL02-RF02 5.0 Non-Interventional Study Protocol Template For Secondary Data Collection Study 01-Aug-2023 Page 41 of 72

Table 2Number of Individuals Needed to Detect Different Rate Ratios for Selected
Outcomes with a Range of Background Rates

Outcome	Background rate	Background rate	Incidence rate	Samp	Sample size		
	per 100,000 person-years ^a	per person during risk interval ^b	ratio	Vaccinated cohort	Unvaccinated cohort		
			5	148	148		
			10	54	54		
	5,000	0.0500000	2	471	471		

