			3	157	157		
			5	59	59		
			10	22	22		

Notes:

a. Due to a lack of published background incidence rates of outcomes of interest among the study-specific population (i.e., adults aged 60 and older who are immunocompromised or renally impaired or hepatically impaired), background rates of outcomes among adults aged 60 and older from general European populations ,published in Supplement 1, Table 1 of Willame et al (2023)⁵³ using VAC4EU databases were used as the basis of sample size and power calculations. A range of background rates were used to address potential differences in underlying rates between the general and study-specific populations (i.e., higher and lower background incidence rates of outcomes than were published in Willame et al.). Sample size and power calculations may be updated during the study as new and relevant background rate data emerges. Key study design features will be reviewed in the light of any updated sample size and power calculations.

b. Assuming a two-sided alpha = 0.05, power of 80%, and a ratio of 1:1 of vaccinated to unvaccinated. Examples of background IR accounting for the risk window:

Anaphylaxis (10/100,000 person-years)/365 * risk window (risk window 2 days) = 0.0000005

GBS (6/100,000 person-years)/365 * risk window (risk window 42 days) = 0.0000069

Arrhythmia (2,000/100,000 person-years)/365 * risk window (risk window 365 days) = 0.02

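### Heart failure, stress cardiomyopathy, ARDS, death and arrhythmias other than atrial fibrillation/supraventricular have only a single 365-day cohort rate ratio, which dilutes an excess in the first weeks

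*Protocol*

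**What the plan says.** Table 1 (Protocol 9.3.2.1) assigns a window of 1-365 days to type 1 diabetes, narcolepsy, arrhythmia, coronary artery disease, heart failure, microangiopathy, stress cardiomyopathy and ARDS, and 0-365 days to death. All nine are marked for the cohort design only. Section 9.2.4 sets the limit on follow-up: "Patient follow-up will last for up to 12 months post-vaccination depending on the outcome".

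Section 9.7.3.1 compares the cohorts by weighted Poisson regression over follow-up truncated at the end of the risk window, with no split of time. Section 9.7.2 adds Kaplan-Meier and adjusted parametric cumulative incidence for outcomes with unknown windows or needing longer follow-up, with death as its example.

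On alternative windows in the cohort design, section 9.7.4 lists "Comparative cohort design with extended risk windows for the acute outcomes to assess potential outcome under-reporting and misclassification". It makes one exception: windows of 0-3, 0-1 and 0-30 days for atrial fibrillation and supraventricular arrhythmias, with an optional SCRI on the same intervals. Note e to Table 1 commits to the 0-3 day analysis.

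The study-size example for arrhythmia uses the full year: "Arrhythmia (2,000/100,000 person-years)/365 * risk window (risk window 365 days) = 0.02". On the disease itself, section 7 says "RSV illness commonly occurs in individuals with existing comorbidities, which are exacerbated due to RSV exposure".

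**The concern.** An acute reaction to a vaccine would be expected in the first days or weeks. Averaging it over a year mixes a short period of possible excess with a long period of none. The later months also include RSV seasons in which vaccination may prevent RSV-triggered cardiac, respiratory and fatal events, so the year-long IRR is a net of early harm and later benefit.

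The protocol recognises rapid onset as a reason to start some intervals on day 0 (note g to Table 1, attached to death among others), yet death then receives one 365-day average. Section 9.9 accepts that uncertain risk periods can attenuate estimates and promises to vary them, but no listed analysis shortens the window for these outcomes. The item that extends windows does not help, since follow-up already stops at 12 months. The stake is sensitivity to early harm in populations whose safety profile the protocol calls unknown.

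**Working it through.** **Inputs from section 9.5.** "assuming a two-sided alpha level of 0.05"; "a power of 80% across a range of IRRs"; "an equal number of individuals for the vaccinated and unvaccinated cohorts". For the rate: "This assumes a background rate of 2,000 arrythmia events per 100,000 person-years among the unvaccinated individuals", which is 0.02 per person over 365 days.

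**Reproducing Table 2.** For two Poisson rates, n = (z0.975 + z0.80)² × (L0 + L1)/(L1 − L0)² per cohort, with (1.960 + 0.8416)² = 7.849. With L0 = 0.02 and L1 = 0.04, n = 7.849 × 0.06/0.0004 = 1,177.3, rounded up to 1,178, as stated. IRRs of 3, 5 and 10 give 393, 148 and 54. A rate of 0.05 gives 471, 157, 59 and 22. All eight match. These figures assume one constant IRR for the whole year.

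**Dilution.** Let the true IRR be r for the first w days and 1 afterwards, with uniform background hazard and complete follow-up. Then IRR365 = 1 + (r − 1) × w/365. For r = 2:
- w = 42: 1 + 42/365 = 1.115
- w = 30: 1 + 30/365 = 1.082
- w = 28: 1 + 28/365 = 1.077

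This does not depend on the background rate.

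**Sample size for the same early doubling, rate 0.02 per year.**

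| Excess confined to | n per cohort, 365-day IRR | n per cohort, matching early window | Ratio |
|---|---|---|---|
| 42 days | 62,689 | 10,232 | 6.1 |
| 30 days | 120,960 | 14,325 | 8.4 |

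For 42 days, the year-long analysis has L0 = 0.02 and L1 = 0.0223, and the early window has L0 = 0.02 × 42/365 = 0.00230 and L1 = 0.00460. Writing f = w/365, the ratio is [2 + (r − 1)f]/[f(1 + r)] = 2.115/0.345 = 6.1. The background rate cancels: at 0.05 per year the figures are 25,076 and 4,093, again 6.1.

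**Power for the 42-day doubling, rate 0.02.** Power = Φ(|L1 − L0|/√[(L0 + L1)/n] − 1.96).
- At 10,232 per cohort: 20% on the 365-day IRR, 80% on the early window.
- At Table 2's 1,178 per cohort: 6% on the 365-day IRR. The early window gives Φ(0.00230/√(0.00690/1,178) − 1.96) = Φ(−1.01), about 16%. Neither is adequate at that size.

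**Adding a later benefit (assumed; the protocol gives no figure).** With a later IRR of b from day w to day E, IRR365 = [r·w + b(E − w) + (365 − E)]/365. For r = 2:

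| w | E | b = 0.95 | b = 0.90 | b = 0.80 |
|---|---|---|---|---|
| 30 | 365 | 1.036 | 0.990 | 0.899 |
| 30 | 180 | 1.062 | 1.041 | 1.000 |
| 42 | 365 | 1.071 | 1.027 | 0.938 |
| 42 | 180 | 1.096 | 1.077 | 1.039 |

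Whether the year-long IRR falls below 1 depends on how large and how long the benefit is assumed to be. The dilution needs no such assumption.

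**The case against.** A reader might infer that all nine year-long outcomes lack any early contrast. The documents do not support that. Atrial fibrillation and supraventricular arrhythmias have named short windows. For type 1 diabetes the protocol itself notes a lag from symptoms to diagnosis, and for narcolepsy too a long window is defensible. The case is less clear for coronary artery disease and microangiopathy. Table 1 also gives acute cardiovascular injury 1-28 days, and the same to a coagulation composite that includes myocardial infarction and ischaemic stroke. How far these overlap the long-window outcomes depends on algorithms left to the SAP.

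The section 9.7.2 curves would show an early divergence, so timing is not invisible. They do not fix an early rate ratio, and an early window chosen after seeing them would be post hoc.

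The list in section 9.7.4 is open and defers detail to the SAP, which could add short windows. That carries weight. But the year-long window and the cohort-only approach are fixed in the protocol, and neither the open list nor section 9.9's general promise supplies an early contrast for these outcomes.

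The sample sizes rest on arrhythmia, and the protocol gives no rates for heart failure, stress cardiomyopathy or ARDS. The absolute numbers therefore do not transfer to those outcomes; the dilution and the 6.1-fold ratio do.

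Finally, section 9.7.4 recognises that vaccination may be deferred while a person is unwell. That would depress early rates, especially of death, in the vaccinated. It is a sound reason not to rest the safety conclusion on the early IRR alone.

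**Conclusion.** The point holds for heart failure, stress cardiomyopathy, ARDS, death and arrhythmias other than atrial fibrillation/supraventricular, and less clearly for coronary artery disease and microangiopathy. For these the only planned comparative estimate is a 365-day cohort IRR. A doubling confined to the first 30-42 days would read as 1.08-1.12 and need about 6 to 8 times as many people per cohort to detect as on a matching early window.

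This assumes a uniform background hazard, complete follow-up and no effect after the early window. If the hazard is higher in the weeks after vaccination, or later follow-up is lost to censoring, the early period weighs more and the dilution is somewhat less.

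It would go too far to say that early harm would be reported as no increased risk, or that the year-long IRR would fall below 1. The objective is estimation, section 9.7 leaves the excess-risk threshold to the SAP, and the size of any RSV-related benefit is not given. This is a cheap and worthwhile improvement to the plan; it does not show that the 365-day analysis is invalid.

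**What to change.** In sections 9.3.2.1 and 9.7.4, prespecify for the acute-onset 365-day outcomes and death a weighted Poisson IRR in two nested periods: an early window (for example to day 28, as for acute cardiovascular injury, or to day 42) and the remainder to day 365. Report both beside the 365-day IRR, and describe the latter as a net effect that can include prevented RSV disease.

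State that the early IRR is read together with the 365-day IRR and the negative-control outcome results, and is not the sole basis for the safety conclusion. Type 1 diabetes and narcolepsy can keep the long window alone.

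The cost is wording and a time split of data already extracted; no new data are needed. The downsides are more estimates to report, wider early-window intervals for rare outcomes, and possible early healthy-vaccinee bias.
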